1 INTRODUCTION/BACKGROUND

Total knee arthroplasty (TKA) and total hip arthroplasty (THA) are highly effective interventions for end-stage arthritis of the knee and hip. Controlling postoperative pain and nausea after total joint arthroplasty remains an important challenge. Perioperative corticosteroids are safe, facilitate earlier discharge, and improve patient recovery following unilateral total knee arthroplasty and total hip arthroplasty. Higher doses (15-20 mg of dexamethasone) are associated with further reductions in dynamic pain and PONV, and repeat dosing may further reduce LOS. It was found that neither one nor two doses of 24 mg intravenous dexamethasone demonstrated prolonged effects on overall pain or sleep quality on postoperative days 3-7 after total knee arthroplasty, also have no effect on patients satisfaction, but it reduced the opioid consumption. Tranexamic acid (TXA) reduces rates of blood transfusion for total hip arthroplasty (THA) and total knee arthroplasty (TKA). Hence, it was proved that the combination of TXA and DEX has positive impacts on the usage of oxycodone and metoclopramide, postoperative range of motion, postoperative nausea and vomiting and reduces the length of hospital stay. The administration of 10 mg dexamethasone 1 h before the surgery, and repeated at 6 h postoperatively can significantly reduce the level of postoperative CRP and IL-6. There is insufficient evidence on perioperative dexamethasone in primary TJA to determine the optimal dose, number of doses, or risk of postoperative adverse events.

2 .Background of interventional procedure

Total joint arthroplasty (TKA) is viewed as one of the most successful orthopedic surgeries for most end-stage joint diseases. In recent years, the concept of enhanced recovery after surgery (ERAS) has greatly improved the speed of rehabilitation after total joint arthroplasty. Patients feel more comfortable during the perioperative period and have shorter hospital stays with the administration of steroid administration. Dexamethasone plays an important role in ERAS due to its anti-inflammatory and pain reduction role. As, TXA can prevent the activation of plasminogen and delay fibrinolysis and reduce blood loss and the rate of blood transfusion perioperatively. Recent studies showed that dexamethasone may be administered multiple times peri operatively. A large number of studies confirmed that dexamethasone can reduce post operative pain and inflammation and shortens the length of hospital stay and combination pre operative tranexamic acid with dexamethasone reduces the limb swelling that improves the joint range of motion. There will be no risk of the interventional drug

Benefits will include that the drug is cost effective, easily available, reduce the post operative complications

3. Rationale

Previous studies showed the effects of peri-operative use of single dose of dexamethasone, and there is very little data available on effects of peri-op use of multiple doses of dexamethasone. There is no study that has been conducted yet, which compared the effects of peri-op use of 1 dose of dexamethasone and tranexamic acid with 2 doses of dexamethasone and tranexamic acid, on post operative range of motion and pain during rest and weight bearing on operated limb, length of stay in hospital and C-reactive protein.

4. Study Objectives

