5.2 Study setting & target population

Study settings: Orthopedics Department, Indus Hospital and Health Network.

Targeted Population: patients having knee/hip osteoarthritis scheduled for joint replacement of one or both sides.

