7 STUDY TREATMENT (OR INTERVENTION)

7.1 Regimens (or Intervention), Administration, and Duration

All patients will randomize into two groups,

Group A: 1 dose of IV Dexamethasone 10mg+ tranexamic acid (20 mg/kg);

Group B: 2 doses of IV Dexamethasone 10mg+ tranexamic acid 20 mg/kg.

In group A, 1 dose of 10 mg of intravenous dexamethasone and 20mg/kg of intravenous tranexamic acid administered at 10 minutes before surgery.

In group B, dose of 10 mg of intravenous dexamethasone and 20mg/kg of intravenous tranexamic acid administered at 10 minutes before surgery and then 10mg of intravenous dexamethasone will be again administered before incision closure.

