12 ADVERSE EVENTS DATA MANAGEMENT & REPORTING

12.1 Safety Definitions

12.1.1 Adverse Event (AE):

Not any

12.1.2 Adverse Reaction:

Not any

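### Section 2 says the study drug carries no risk, against section 1, and 12.1 leaves the adverse event definitions empty while 9.1 and 11.6 act on toxicity and serious adverse events

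*Protocol*

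**What the plan says.** **Risk.** Section 2 (Background of interventional procedure) states that "There will be no risk of the interventional drug". Section 1 ends with: "There is insufficient evidence on perioperative dexamethasone in primary TJA to determine the optimal dose, number of doses, or risk of postoperative adverse events". Section 1 also contains a favourable general statement: "Perioperative corticosteroids are safe, facilitate earlier discharge, and improve patient recovery following unilateral total knee arthroplasty and total hip arthroplasty".

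**The randomised contrast.** Under 7.1, both groups receive dexamethasone 10 mg and tranexamic acid 20 mg/kg ten minutes before surgery. In group B, "10mg of intravenous dexamethasone will be again administered before incision closure".

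**Safety definitions.** Section 12.1 has two headings, adverse event (12.1.1) and adverse reaction (12.1.2). The entry under each is 'Not any'.

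**Rules that act on harm.** Section 9.1 ends treatment for drug-related toxicity, and for reasons the physician considers life-threatening even where a toxicity section does not cover them. Section 9.2 allows withdrawal at the discretion of the primary care provider, the investigator or the IRB. Section 11.5 provides for telephone calls to establish health status after missed visits. Section 11.6 requires safety follow-up of patients who leave the trial because of a serious adverse event, among other reasons.

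**Data collection.** Section 11.2 trains nursing staff on CRP, range of motion, fatigue, length of stay and pain. Section 8.3 lists a fatigue scale and a pain scale. Sections 11.3 and 14 list four forms (before surgery, day 1 after surgery, and weeks 1 and 4 after discharge), the latter by file name only.

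**The concern.** The only planned difference between the arms is a second steroid dose. A protocol that calls the risk of that choice unresolved cannot also state that there is none. Investigators, the IRB and anyone drafting patient information from the protocol would be working from a risk position that its own background does not support.

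The second part is practical. Sections 9.1 and 11.6 tell staff to act when certain harms occur, but the section meant to define harms gives them nothing to apply. Two members of staff could reasonably disagree on whether an event is an adverse event, is drug-related or is serious, and the protocol would not settle it. If events are judged or noted inconsistently, the trial could end with little usable safety information on the extra dose, which is one of the questions section 1 leaves open.

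**Working it through.** No stated figure needs to be reproduced here. The check sets the sections side by side and counts.

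**1. Section 2 against section 1.** Section 2 makes an unqualified statement of no risk. The last sentence of section 1, immediately before section 2, says that number of doses and adverse event risk cannot yet be determined. An undetermined risk is not a zero risk, so the two cannot both stand. The general statement in section 1 that corticosteroids are safe does not reconcile them: safe is weaker than free of risk, and section 1 still closes by leaving the risk open.

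**2. How this bears on the contrast.**
- Group A: 1 × 10 mg = 10 mg dexamethasone.
- Group B: 2 × 10 mg = 20 mg dexamethasone.
- Planned patients (10.3): 46 + 46 = 92, so 46 are planned to receive the second dose.

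**3. Section 12.1.** Two headings, two entries of 'Not any': 0 of 2 definitions have content. The words are printed in the text and are not a redaction or a gap from extraction.

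**4. Terms on which action depends.**

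| Section | Action | Term that triggers it | Defined in the protocol? |
|---|---|---|---|
| 9.1 | Stop treatment | Drug-related toxicity | No |
| 11.6 | Safety follow-up | Serious adverse event | No |

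So 0 of 2 are defined. The second gap is separate from the first: 12.1 has no heading for serious adverse events, so completing its two headings would still leave 11.6 without a definition.

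**5. Practical reach of 9.1.** Both groups receive the first dose before surgery begins. The dexamethasone that can still be withheld after that is group B's second dose, so the undefined toxicity trigger mainly concerns that dose. Section 11.6 reaches further, because it applies through follow-up in both arms.

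**6. Collection.** Adverse events appear in neither the training list in 11.2 (0 of its five items) nor the questionnaires in 8.3 (0 of 2). The content of the four forms cannot be read from the document, so the check stops there.

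**7. Size of harm.** The protocol gives no adverse event rate, and none is assumed here.

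**The case against.** The best defence is that dexamethasone at these doses is familiar, and the protocol says so. Section 1 refers to 15-20 mg, to one or two doses of 24 mg, and to 10 mg repeated six hours after surgery; section 2 adds that repeated perioperative dosing has been used. On that account 20 mg is within studied doses. Moreover, 'Not any' is this document's habitual filler (5.5 to 5.8, 7.2.2, 7.2.3) and in 12.1 may mean only that no events are anticipated. Safety action does exist in 9.1, 9.2, 11.5 and 11.6.

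Much of this stands, and it limits the point. It does not rescue the no-risk sentence, because section 1 mentions those doses and still calls the risk undetermined. Even if 12.1 means that no events are expected, it supplies no definition. Nor can this be left to a statistical analysis plan: these definitions direct clinical staff during conduct, and the protocol has a section for them.

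Several stronger readings are tempting but not supported:
- **Harms go unrecorded.** The forms are not shown, so this cannot be concluded.
- **The protocol recognises no adverse events.** Sections 9.1 and 11.6 recognise toxicity, life-threatening reasons and serious adverse events. The defect is in definition.
- **Section 3 is also contradicted.** It says "there is very little data available on effects of peri-op use of multiple doses of dexamethasone" and then names the outcomes it has in mind: range of motion, pain, length of stay and CRP. That is a gap in efficacy evidence and does not speak to harm.
- **The safety statement excludes bilateral surgery.** Section 1 names unilateral knee replacement and hip replacement, and 5.2 admits patients "scheduled for joint replacement of one or both sides", but section 1 says nothing adverse about bilateral surgery. There is no conflict.
- **The week 1 and week 4 visits cannot be safety visits.** Section 7.3 mentions outcome assessment while defining compliance; 8.1.3 sets the visits without limiting their purpose.
- **The missing toxicity section disables 9.1.** That clause lets the physician stop treatment on clinical judgement whether or not the section exists.

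**Conclusion.** The point holds as a contradiction about risk and a gap in safety definitions. Section 2 asserts what section 1 says is unknown, on the very variable being randomised. Neither definition in 12.1 has content, and neither of the two terms that trigger action in 9.1 and 11.6 is defined. The rules apply to all 92 planned patients, and the open question of risk bears most on the 46 planned for group B.

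It should be corrected, on grounds of patient safety and internal consistency. It does not touch randomisation, the sample size or the listed efficacy outcomes, and the practical reach of 9.1 is small. The conclusion rests on the printed text alone, with one reading assumed: that the drug meant in section 2 includes dexamethasone, which that section discusses and whose dosing the trial compares. Whether adverse events are already captured on the forms remains open.

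**What to change.** 1. Delete the no-risk sentence in section 2 and state instead that the adverse event risk of the second dose is not established.
2. Replace 'Not any' in 12.1.1 and 12.1.2 with working definitions of adverse event and adverse reaction, and add a definition of serious adverse event. Have 9.1 and 11.6 refer to these. The clinical content is for the investigators to settle.
3. Record adverse events at day 1, week 1 and week 4 on the existing forms, adding one item if none is there, so that they can be reported by arm. The form need not show the arm, which keeps the data collectors blinded as 10.1 intends.
4. Add adverse event recording to the training list in 11.2.
5. As tidying only, remove the reference in 9.1 to a toxicity section that the protocol does not contain.

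The cost is a short amendment and at most one added form item, with no extra visits.

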4.1 Primary Objective

To evaluate the effectiveness of peri operative intravenous 2 doses of dexamethasone in lower limb joint/s replacement surgeries on postoperative C-reactive protein, post operative fatigue, postoperative joint range, post operative pain during rest and weight bearing, and length of hospital stay.

4.2 Hypothesis:

If hypothesis will get confirmed, then the peri operative use of 2 doses of dexamethasone with intravenous tranexamic acid, reduces the postoperative C-reactive protein, post operative fatigue, pain during rest and weight bearing, and length of hospital stay and improves the post operative joint range of motion.

If hypothesis will not get confirmed, then the peri operative use of 2 doses of dexamethasone with intravenous tranexamic acid, will not reduces the postoperative C-reactive protein, post operative fatigue, pain during rest and weight bearing, and length of hospital stay and and will not improve the post operative joint range of motion.

5. Material and Methods:

5.1 Study Design:

Randomized controlled trial with 2 arms

Arm 1: GROUP A will receive 1 dose of dexamethasone (10mg) with tranexamic acid (20mg/kg), peri operatively .

Arm 2: GROUP B will receive 2 doses of dexamethasone (2*10mg) with tranexamic acid (20mg/kg), peri operatively.

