8.2 Laboratory Evaluations

Pre Operative laboratory evaluations will include:

Complete Blood Count (CBC)

C-Reactive Protein (CRP)

Renal Function Test (RFT)

Hepatitis B and C

Electrocardiogram

Chest X-ray

Activated Partial Thrombin Time (aPTT)

Prothrombin Time (PT)

Hemoglobin A1c (HbA1c)

Post operative laboratory evaluations

Complete Blood Count (CBC)

C-Reactive Protein (CRP)

from which investigators will take data of C-reactive protein values in our study, to compare pre and post operatively.

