8.3 Questionnaires

- Post operative identity consequences fatigue rating scale
- Numeric Pain rating Scale

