10.3 Determination of Sample Size and Power Calculation

The calculated sample size, using total blood loss is 25 in each group and after adding 20% dropout the sample size will be $25+5=30$ in each group. The sample size is calculated using following information.

$Z_{1-\alpha/2}$ Level of significance=95%

μ_1 Expected mean change in total blood loss in Group A=93.80

μ_2 Expected mean change in total blood loss in Group B= 95.98

δ_1 Expected standard deviation in group A=3.88

δ_2 Expected standard deviation in group B=2.82

$Z_{1-\beta}$ power of the study= 80%

sample size in a group(n)= 38

After adding 20% drop out $38+8=46$ in each group.

Total sample size will be 92

No of groups/arms in study:

Type of comparison:

Superiority comparison

Type of configuration:

Parallel designs

Level of significance (Alpha level): 95 %

Power: 0.8 or 80 %

Allocation ratio: 1:1

Underlying population event rate:

Almost 90 percent of population undergoing total joint replacement, whether uni or bilateral would show the positive clinical outcomes with the use of 2 doses of dexamethasone.

Effect size of therapy: the clinical guidelines shows that each group of clinical trial must have at least 30 participants, so effect size is 92 more than sample size calculated, drop out patients percentages added.

Estimated loss to follow-up or refusals: Based on previous work in this population, 20 % will be lost to follow up or drop out from the trial.

10.4 Underlying population event rate:

The population enrolled in previous studies undergoing total joint replacement, whether unilateral or bilateral showed the positive clinical outcomes with the use of dexamethasone with tranexamic acid.

10.5 Estimated loss to follow-up or refusals: Based on previous work in this population, 20 % will be lost to follow up or drop out from the trial.

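### Section 4.1 names six primary outcomes without saying which decides the trial, and the only 80% power, in section 10.3, is for total blood loss, which is not among them

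*Protocol*

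**What the plan says.** The primary objective (Protocol 4.1) is to evaluate two doses of dexamethasone "on postoperative C-reactive protein, post operative fatigue, postoperative joint range, post operative pain during rest and weight bearing, and length of hospital stay". None of these outcomes is ranked. Section 4.2 carries the same list into a single hypothesis, with one branch for confirmation and one for non-confirmation.

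Section 11.3 plans records before surgery, on the first postoperative day, and at weeks 1 and 4 after discharge. No time is marked as the deciding one.

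The sample size is in section 10.3, under a "Superiority comparison". It opens with "The calculated sample size, using total blood loss is 25 in each group", then lists means and SDs for total blood loss, gives "sample size in a group(n)= 38", and ends with "After adding 20% drop out $38+8=46$ in each group", 92 in total. No difference or SD is given for any outcome in 4.1.

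Outside 10.3, blood loss is mentioned only in section 2, as something tranexamic acid reduces. Both arms receive tranexamic acid at the same dose. The instruments in 8.3 are a fatigue scale and the "Numeric Pain rating Scale". The data that nursing staff are trained to collect (11.2) are CRP, knee range, fatigue, length of stay and pain. On the laboratory tests, 8.2 adds: "from which investigators will take data of C-reactive protein values in our study, to compare pre and post operatively".

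**The concern.** A power statement tells the reader how likely the trial is to answer its own question. Here the question (4.1) and the power statement (10.3) concern different variables, so the 80% cannot be carried over to CRP, fatigue, range, pain or length of stay.

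With six unranked outcomes, several of them measured more than once, this protocol also leaves open which result counts as the trial's answer. As far as this document goes, that choice could be made after the data are seen. Section 4.2 does not close the gap. It describes success on everything and failure on everything, but not the mixed pattern in between.

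**Working it through.** **1. Reproducing the plan's figure.** Inputs from 10.3: means 93.80 (Group A) and 95.98 (Group B), SDs 3.88 and 2.82, power 80%, 1:1 allocation. The level is written as 95%; I read it as two-sided alpha 0.05 because the term is labelled as the 1−α/2 quantile.

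- Difference: 95.98 − 93.80 = 2.18.
- n per arm = (1.960 + 0.842)² × (3.88² + 2.82²) / 2.18² = 7.849 × 23.007 / 4.752 = 37.997, so 38.
- Standardised difference: 2.18 / √(23.007/2) = 2.18 / 3.392 = 0.643.

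So 38 is right for these inputs. The other figure, 25, is not:

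- Power at 25 per arm: Φ(2.18/√(23.007/25) − 1.960) = Φ(2.272 − 1.960) = Φ(0.312), about 62%.
- Two more lenient readings also miss 25: one-sided 0.05 gives 30, and using the smaller SD in both arms gives 27.

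**2. Does that variable belong to the objective?** The lists in 4.1, 4.2, 8.3 and 11.2, set beside 10.3, share no entry with total blood loss. The 80% belongs to the blood-loss inputs alone.

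**3. What 92 patients can detect on a listed outcome.** No effect or SD is given for any of the six, so only standardised effects can be stated (two-sided 0.05, 80% power, before any gain from baseline adjustment).

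- After 20% loss: 46 × 0.8 = 36.8 per arm; 2.802 × √(2/36.8) = 0.653 SD.
- All 46 evaluable: 2.802 × √(2/46) = 0.584 SD.

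Power of a two-sample t-test at assumed true effects:

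| Effect (SD) | 37 per arm | 46 per arm |
|---|---|---|
| 0.3 | 25% | 30% |
| 0.5 | 56% | 66% |
| 0.8 | 92% | 97% |

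**4. Illustration of the 4.2 gap.** Assume all six must succeed, each has 80% power, and the six test statistics are normal with a common correlation ρ. Then P(all six) = ∫ [Φ((0.842 + √ρ·u)/√(1−ρ))]⁶ φ(u) du.

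| ρ | All six succeed | Some but not all |
|---|---|---|
| 0 | 0.8⁶ = 26% | 74% |
| 0.5 | 48% | 50% |
| 0.9 | 68% | 22% |

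Even with every effect real, a mixed result is common on these assumptions, and 4.2 gives no reading for it.

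**The case against.** **The blood-loss label may be a slip.** The inputs have no unit, and the mean is higher in the two-dose arm, which is odd for blood loss in a superiority trial of two doses. Of the six outcomes, only joint range is hypothesised to rise. This is a fair point, and the document cannot settle it. If it is a slip, 10.3 still needs correcting, and 4.1 still names no deciding outcome.

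**The statistical analysis plan may deal with it.** Multiplicity control and the reading of mixed results can be left there. The choice of primary outcome and the basis of the sample size are stated in this protocol, and they do not match. An unseen plan does not remove that.

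**Blood loss may be recorded after all.** A reader might infer that it is never collected. The text does not go so far. Section 8.2 lists a postoperative blood count and does not say that CRP is the sole value taken, and the four data forms are not shown. Even if recorded, blood loss is still outside the objective.

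**The timing gap is narrower than it looks.** Length of stay is a single value, and 8.2 gives CRP a before-and-after comparison, though without naming the postoperative day. The gap is clearest for fatigue, range and pain.

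**Other designs are legitimate.** Co-primary outcomes, a hierarchy or a split alpha would also resolve the ambiguity. That is true; a single primary is the simplest choice at this sample size.

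**Conclusion.** The point holds. The protocol designates no deciding outcome, and its 80% power is not supported for any outcome it lists. The arithmetic for 38 per group is sound for the blood-loss inputs; the 25 in the same section is not.

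Three stronger readings are not supported:

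- *The trial is underpowered for its outcomes.* Power for the six is unknown. At 92 patients it would reach 80% for a true effect of about 0.58 to 0.65 SD, and nothing in the protocol shows whether the real effects are larger or smaller.
- *False-positive risk is inflated.* If any one success counted, with 2.5% in the favourable direction on each, the risk of a false claim of benefit would be 1 − 0.975⁶ = 14% at zero correlation and about 5% at 0.9. But 4.2 joins the outcomes with a conjunction and states no such rule. Requiring all six would not inflate the error.
- *The plan will claim absence of effect.* The second branch of 4.2 opens "If hypothesis will not get confirmed, then the peri operative use of 2 doses of dexamethasone with intravenous tranexamic acid, will not reduces the". Taken as a rule for reading a non-significant result, it would need an equivalence margin. It reads more naturally as the null half of a hypothesis pair, so I do not press this.

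The 26% to 68% range rests on an assumed all-six rule, an assumed 80% power for each outcome, and assumed correlations of 0 to 0.9. It illustrates the gap and does not estimate this trial's power.

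**What to change.** - **4.1:** name one of the listed outcomes as primary (the sponsor's choice), with one of the planned times where it is measured repeatedly. Make the other five secondary.
- **4.2:** replace the two branches with a rule such as: *Superiority of two doses over one is concluded if the primary endpoint favours Group B at two-sided 0.05; otherwise superiority was not shown. Each other outcome is reported as a between-arm difference with its 95% confidence interval.*
- **10.3:** correct or replace the blood-loss variable so that the calculation is for the primary endpoint, with its expected difference and SD, and delete the 25-per-group figure. Keep 92 patients and restate either the power or the detectable effect: about 0.65 SD at 80% power with about 37 evaluable per arm, or about 0.58 SD if the endpoint is in hospital and all 46 are evaluable.

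The cost is rewording and one new calculation, with no extra patients and no new data collection. Five outcomes lose primary status, and the stated power may fall below 80% once it is computed for a listed outcome.
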